9.2.2 Serious adverse events (SAEs)

A serious adverse event is any untoward medical occurrence or effect that

- results in death;
- is life threatening (at the time of the event);
- requires hospitalisation or prolongation of existing inpatients' hospitalisation;
- results in persistent or significant disability or incapacity;
- is a congenital anomaly or birth defect; or
- any other important medical event that did not result in any of the outcomes listed above due to medical or surgical intervention but could have been based upon appropriate judgement by the investigator.

An elective hospital admission will not be considered as a serious adverse event.

The investigator will report all SAEs to the sponsor without undue delay after obtaining knowledge of the events.

The sponsor will report the SAEs through the web portal ToetsingOnline to the accredited METC that approved the protocol, within 7 days of first knowledge for SAEs that result in death or are life threatening followed by a period of maximum of 8 days to complete the initial preliminary report. All other SAEs will be reported within a period of maximum 15 days after the sponsor has first knowledge of the serious adverse events.

9.2.3 Suspected unexpected serious adverse reactions (SUSARs)

Not Applicable

9.3 Annual safety report

Not applicable

9.4 Follow-up of adverse events

All AEs will be followed until they have abated, or until a stable situation has been reached. Depending on the event, follow up may require additional tests or medical procedures as indicated, and/or referral to the general physician or a medical specialist.

SAEs need to be reported till end of study within the Netherlands, as defined in the protocol.

9.5 Data Safety Monitoring Board (DSMB)

According the risk classification (K6.), this study has a negligible risk. Therefore we will not be appointing a DSMB.

10. STATISTICAL ANALYSIS

All data that will be collected in this study will result in (or be transformed into) quantitative data and will either be categorical or continuous. Normal distributions will be checked by visual inspection of histograms and QQ plots. Normally distributed variables will be described as mean with standard deviation (SD) and non-normally distributed variables will be described as median with interquartile range (IQR). Categorical variables will be described as numbers (N) and percentages. As we collect data on patterns, we will descriptively present all patterns derived in line graphs to visually inspect pattern differences between interventions. Missing data will be interpolated/imputed with a standard algorithm in SPSS/ R Software.

10.1 Primary study parameter

The primary study endpoint will be change in insomnia severity measured by the ISI. We will perform a paired t-test (assuming normally distributed data) to examine the difference between active morning and active evening. Data will be shown as mean difference, SD (or 95% confidence interval), and p-value. A p-value lower than 0.05 will be considered as statistically significant.

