3. STUDY DESIGN

We will perform a randomized two-armed cross-over study. Both groups will start with the sedentary period. Randomization will be performed at the moment of enrollment using a computer-based statistical program (depending on the intervention arm, participants will then undergo the active morning intervention or active evening intervention first, followed by the remaining intervention. There will be a total of two washout periods both lasting 7 days, one between the sedentary period and first intervention and one between the first and second intervention to prevent or minimize 'carry over' of previous intervention effect. The two interventions and the sedentary period will last 14 days each and contain a 'calibration period' (7 days) and a 'measurement week' (7 days). The former will serve as an adjustment period in which we hypothesize that our endpoints of interest will adjust to the new exercise regimen. After the calibration period, the measurement week starts in which all endpoints will be measured. Apart from the measurements, there are no differences in intervention between calibration and measurement week. The total study duration will be 8 weeks and the study will largely take place at the participants' home except for the training sessions (Vitality Clubs) that will take place at an outdoor sports facility in the municipality of Leiden and the study site visits which will take place in the LUMC. **Figure 3.1** shows a schematic overview of the study outline and **Appendix A** shows an example of the study schedule during the active morning intervention.

[figure not shown]

Figure 3.1. Schematic overview of the study

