3.1 Design justification

A cross-over study allows the response of a participant to morning exercise to be contrasted with the same participant's response to evening physical activity and sedentary period. Removing inter-participant variation allows for more efficient and precise estimation than similar sized studies with parallel intervention groups.

As we study the effect of timing on change in insomnia severity and changes in the rhythm of multiple processes hypothesized to be altered rapidly through environmental cues, such as daylight changes over the season, a randomized cross-over study which is usually bound to short-term outcomes is the most suitable design for this study.

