4.4 Sample size calculation

The sample size was calculated for the primary outcome of mean change of insomnia symptoms severity from baseline and after completing the active morning vs. active evening measured by the ISI which is proven to be a well validated and sensitive questionnaire for mapping insomnia severity. All sample size calculations were based on statistical power of 0.80 and a 2-sided α of 0.05. The calculations were performed using GPower v.3.1 (Kiel University, Germany). To the best of our knowledge, there is no literature available on the effect size of physical activity timing on insomnia severity. Therefore, estimations were based on treatment effect size of guideline recommended physical activity on insomnia severity (measured by ISI) found in a previous randomized controlled trial(32). Assuming a standard deviation (SD) of 5.4, a total of 36 participants are required to detect a minimal difference of 2.6 points on the ISI. Considering a possible dropout rate of 10% during the study, the target sample size is 40 participants.

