
5.1.1 Sedentary period

Literature shows that physical activity improves insomnia severity.(32) In previous studies, the follow-up period was at least 3 months. As we will use a shorter follow-up period in this study, we have included a sedentary period, to assess the effect of physical activity versus no physical activity. This intervention additionally examines the effect of physical activity timing. In order to verify that the exercise intervention provided in this study has a similar positive effect, we will compare our interventions to this sedentary period. All participants will start with a 14-day sedentary period. They will be instructed to refrain from any moderate to vigorous exercise. Compliance to these instructions will be observed through the wrist worn accelerometer. Where necessary, participants will be reminded of the instructions.

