8.2 Randomisation, blinding and treatment allocation

As this is a cross-over study, participants will undergo all three conditions. Participants will be randomised into two groups at enrolment using a computer-based statistical program. Both groups will start with sedentary period where after the first group will start with the active morning first followed by the active evening. For the second group, the order of the two activity interventions will be reversed (sedentary period- active evening- active morning). Blinding will not be possible in this study. However, we will minimise the interference of the researchers that will perform the analyses during the study by hiring a research nurse to lead the study. If necessary, the research nurse will be assisted by medical students.

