8.5 Replacement of individual subjects after withdrawal

If a subject withdraws from the study, the participant will not be replaced; the logistics of this study make it impossible to enter the study once it has started. We have taken this into account with the 10% drop-out rate.

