10.2 Secondary study parameter(s)

Secondary endpoints include changes in:

Biological clock function

- Clockgene expression
- Core body temperature (°C)
 - Diurnal pattern
 - Time of lowest temperature
- Melatonin
 - Dim light melatonin onset (DLMO)

Physiological parameters

- Heart rate
 - Diurnal pattern
 - Average
 - Resting heart rate
 - Minimum/peak heart rate (5 and 95 percentile)
- Heart rate variability (HRV)
- Breathing rate
- Oxygen saturation (SpO2)

Mental health

- Subjective mood
 - Diurnal pattern of:
 - Positive affectivity
 - Negative affectivity
 - Energy
 - Fatigue

- Cognition
- (objective) Electrodermal activity (emotional arousal and stress)

Behavioural factors

- Food intake
 - Frequency
 - Timing
- Habitual sleep (**Table 8.1**)
 - Sleep latency (min)
 - Duration (min)
 - Efficiency (%)
 - Sleep phases (%, min)
 - Awakenings at night (x, min)
 - Rested feeling (subjective, 0-7)
 - General satisfaction with sleep (subjective, 0-7)

Biochemistry

- Glucose metabolism
- Inflammatory markers
- Liver function
- Kidney function
- Thyroid function
- Bone metabolism markers
- White blood cell count

Changes between active morning and active evening will be assessed. Diurnal patterns will be calculated through the hourly mean level of for example glucose and will be displayed for each condition. Additionally, we will perform sensitivity analysis for both the primary endpoint as all secondary endpoints by analyse the changes between the sedentary period & active morning, and the sedentary period & active evening. Assuming the data is normally distributed, a paired t-test will be used for all analyses and data will be shown in as mean difference, SD, and p-value.

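### The primary paired t-test ignores the randomised order of the two active periods, so a period difference would cost precision and, if the sequences end unequal, shift the estimate

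*Combined protocol and SAP*

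**What the plan says.** Sections 3 and 8.2 describe two sequences after a common sedentary period. One group does the morning condition and then the evening condition. "For the second group, the order of the two activity interventions will be reversed". On allocation, section 3 says only this: "Randomization will be performed at the moment of enrollment using a computer-based statistical program". Section 8.2 adds no ratio, block size or balancing rule.

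The primary analysis in section 10.1 is: "We will perform a paired t-test (assuming normally distributed data) to examine the difference between active morning and active evening". Section 10.2 extends the method to the rest: "Assuming the data is normally distributed, a paired t-test will be used for all analyses". The only sensitivity analyses named there compare each active condition with the sedentary period. No section includes period, sequence or order in an analysis.

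The sample size in section 4.4 rests on one line: "Assuming a standard deviation (SD) of 5.4, a total of 36 participants are required to detect a minimal difference of 2.6 points". The target is 40, to allow for 10% dropout. Section 8.5 adds: "If a subject withdraws from the study, the participant will not be replaced".

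**The concern.** A paired t-test on all within-person differences treats the two sequences as one sample. In a two-sequence cross-over, any general change in ISI between the first and second active period pushes the morning-minus-evening difference down in one sequence and up in the other. With equal sequences the mean is unaffected, but the spread between sequences is counted as random error. With unequal sequences the mean moves as well.

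Such a change is plausible. The ISI is completed on the last day of each intervention, so the two active scores are 7 + 14 = 21 days apart. Section 3.1 describes the processes under study as "hypothesized to be altered rapidly through environmental cues, such as daylight changes over the season". Section 8.5 says nobody can join once the study has begun. If participants therefore go through in step (an inference), a seasonal change would act on all of them in the same direction. The 7-day washout is aimed at carry-over and does nothing about a period difference.

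This is the trial's only primary test, and 36 is the smallest number that reaches 80% power, so there is little precision to spare. No planned analysis would show or remove a period effect. Adding the term after seeing the data, in an unblinded study, would be a post hoc choice.

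**Working it through.** **Inputs.** Difference 2.6, SD 5.4, N = 36, two-sided α 0.05, power 0.80, target 40 (section 4.4). Two sequences, allocation rule not stated (section 8.2). No replacement (section 8.5). Assumed, because the documents give no figure: a period shift P (second minus first active period) of 1, 2 or 3 ISI points.

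**Reproducing the plan's figure.** Standardised difference 2.6/5.4 = 0.481. The exact noncentral-t power of a paired t-test is 79.0% at n = 35 and 80.2% at n = 36. Then 36/0.90 = 40. So 36 is reproduced if 5.4 is the SD of the within-person difference. If 5.4 were the SD of single, uncorrelated scores, about 68 would be needed.

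**Effect of a period shift.** Let τ be the true morning-minus-evening difference, σ the within-sequence SD of the differences, and n₁ and n₂ the numbers in the morning-first and evening-first sequences.
- Mean difference: τ − P in morning-first, τ + P in evening-first.
- Bias of the paired mean: P(n₂ − n₁)/N.
- Expected variance of the pooled differences: σ² + 4P²n₁n₂/[N(N − 1)].
- Period-adjusted estimate: the average of the two sequence means, which is unbiased. Its SE is (σ/2)√(1/n₁ + 1/n₂) with N − 2 df.

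For the paired test, the mean is normal with variance σ²/N. Independently, (N − 1)s²/σ² is noncentral chi-square with N − 1 df and noncentrality 4P²n₁n₂/(Nσ²). Power and type I error follow by integration, and simulation agrees.

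**Reading A: σ = 5.4 excludes period spread. Split 18:18, bias 0.**

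| P | SD of pooled differences | Paired power | Adjusted power | Paired type I error |
|---|---|---|---|---|
| 0 | 5.40 | 80.2% | 80.1% | 5.0% |
| 1 | 5.49 | 79% | 80.1% | 4.6% |
| 2 | 5.77 | 76% | 80.1% | 3.7% |
| 3 | 6.20 | 71% | 80.1% | 2.5% |

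**Reading A, unequal splits.**
- 20:16 is the worst split if 20:20 are allocated and the planned 4 drop out. Its chance is 10.6% if dropout is random. A 1-point shift gives bias 1 × 4/36 = 0.11. A 2-point shift gives 2 × 4/36 = 0.22 (8% of 2.6). At 2 points, paired power is 68% or 83% depending on direction, against 80% adjusted; type I error is about 4.2%.
- 22:14 needs unblocked allocation. The binomial chance of a split at least this unequal among 36 is 24%. A 2-point shift gives bias 2 × 8/36 = 0.44 (17% of 2.6). Paired power is 60% or 88%, against 78% adjusted. Type I error is 6.0% and 95% CI coverage about 94%.

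**Reading A, averaged over simple randomisation, P = 1 / 2 / 3.** Bias is 0, type I error about 5%, and power 79% / 75% / 69%. The mean absolute bias in a single trial is 0.13 / 0.26 / 0.40 points.

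**Reading B: 5.4 already includes period spread.** The within-sequence SD is then √(5.4² − P²) = 5.31 / 5.02 / 4.49. At 18:18, paired power is 80.6% / 81.7% / 84.1%, against 81.5% / 85.6% / 92.1% adjusted.

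**The case against.** A paired t-test is a legitimate analysis of a balanced cross-over. At 18:18 it is unbiased and conservative, and averaged over simple randomisation the bias is zero and the type I error about 5%. The 6.0% figure needs unblocked allocation, a 22:14 split and a 2-point shift together. All of this stands: the main loss is precision, not validity. But the trial reports one estimate from one realised split, and the average over hypothetical splits does not correct that estimate.

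The period effect is assumed, and shifts of 2 and 3 points are large beside a target of 2.6 (77% and 115% of it). Section 3.1 mentions daylight to justify a short cross-over; it does not claim that ISI drifts over three weeks. This also stands. At 1 point the harm is small.

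Section 10 says missing data will be imputed. If missing ISI scores were imputed, the analysed split could stay as allocated, and the 20:16 case would weaken. Imputation would not balance an unblocked allocation or recover the precision lost at balance.

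The meaning of 5.4 is not given. If it is a single-score SD, power depends on an unstated correlation. With a 2-point shift at 18:18, paired against adjusted power is about 62% against 66% at correlation 0.3, and 92% against 95% at 0.7. The level changes; the ordering does not.

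Adjustment is not free at every split. With unequal sequences it lowers mean squared error only if the shift exceeds roughly 5.4/√36 = 0.9 points. At 22:14 with no shift it costs about 2 points of power. That is a real but small price.

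**Conclusion.** The concern holds. The plan randomises the order of the two active conditions and then leaves that order out of the analysis. Under reading A with equal sequences, the paired test gives up about 1, 4 and 9 percentage points of power at shifts of 1, 2 and 3 ISI points. Under reading B its power stays above 80% but remains below that of the adjusted test. With unequal sequences the reported estimate carries P(n₂ − n₁)/N of the period effect. Equal sequences are not assured, because no blocking is stated and withdrawals are not replaced.

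The missing term is certain from the text. The size of the harm is conditional on a period effect the documents do not quantify: small at 1 point, material from about 2. Because the remedy costs almost nothing, the change is worth making before the data are seen.

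**What to change.** **Section 10.1.** Pre-specify a linear mixed model for the two end-of-active-period ISI scores, with condition, period (first or second active) and sequence as fixed effects and participant as a random effect. Both changes use the same baseline, so it cancels from the contrast. With complete pairs, the Hills-Armitage two-sample comparison of period differences gives the same test, and the sequence term does not alter the condition estimate. Report morning minus evening with a 95% CI. State how a participant with only one active score is handled, so that the model and the imputation sentence in section 10 agree.

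**Section 10.2.** Use the same model for the morning-versus-evening contrasts of the secondary endpoints only. The sedentary contrasts cannot be period-adjusted, because the sedentary period always comes first: "All participants will start with a 14-day sedentary period". Say so there.

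**Section 8.2.** State 1:1 permuted-block allocation to sequence. The time of randomisation need not move.

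**Cost.** Wording in 10.1 and 10.2 and one line in 8.2; no extra participants, visits or measurements. The model uses one degree of freedom. With no period effect, power goes from 80.2% to 80.1% at 18:18, 79.6% at 20:16 and 78.1% at 22:14. The required 36 and the target of 40 stay as they are.

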10.2 Secondary study parameter(s)

Secondary endpoints include changes in:

Biological clock function

- Clockgene expression
- Core body temperature (°C)
 - Diurnal pattern
 - Time of lowest temperature
- Melatonin
 - Dim light melatonin onset (DLMO)

Physiological parameters

- Heart rate
 - Diurnal pattern
 - Average
 - Resting heart rate
 - Minimum/peak heart rate (5 and 95 percentile)
- Heart rate variability (HRV)
- Breathing rate
- Oxygen saturation (SpO2)

Mental health

- Subjective mood
 - Diurnal pattern of:
 - Positive affectivity
 - Negative affectivity
 - Energy
 - Fatigue

- Cognition
- (objective) Electrodermal activity (emotional arousal and stress)

Behavioural factors

- Food intake
 - Frequency
 - Timing
- Habitual sleep (**Table 8.1**)
 - Sleep latency (min)
 - Duration (min)
 - Efficiency (%)
 - Sleep phases (%, min)
 - Awakenings at night (x, min)
 - Rested feeling (subjective, 0-7)
 - General satisfaction with sleep (subjective, 0-7)

Biochemistry

- Glucose metabolism
- Inflammatory markers
- Liver function
- Kidney function
- Thyroid function
- Bone metabolism markers
- White blood cell count

Changes between active morning and active evening will be assessed. Diurnal patterns will be calculated through the hourly mean level of for example glucose and will be displayed for each condition. Additionally, we will perform sensitivity analysis for both the primary endpoint as all secondary endpoints by analyse the changes between the sedentary period & active morning, and the sedentary period & active evening. Assuming the data is normally distributed, a paired t-test will be used for all analyses and data will be shown in as mean difference, SD, and p-value.

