2. OBJECTIVES

Primary Objective

To examine the effect of physical activity timing on insomnia severity in older adults with self-reported sleep problems.

Secondary Objective

To explore the effect of physical activity timing on rhythmic parameters of biological clock function, physiology and metabolism, mental health, behavioural factors, and immune and cell signalling functions.

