Participants will wear the Corsano Cardiowatch 287-2 (Corsano Health, The Hague, the Netherlands) wrist band on their right wrist continuously during the study period. The wristband is multifunctional and is waterproof. Participants will wear the wrist band 24 hours a day. The HR is measured using a PPG (photoplethysmogram, i.e., optically obtained volumetric measurement) and ECG. The manufacturer supplies the algorithm for converting the PPG/ECG signals into a set of HR values. All data from the Cardiowatch is available real time and is transferred from the watch to the smartphone using a clinical trial app, developed by the provider, which allows the researcher to retrieve live vital sign data while conducting a blinded study. From the app, it will be uploaded to the output server through a HIPAA/AVG compliant cloud service.

Core body temperature

Core body temperature will be continuously measured by the Cardiowatch 287-2. This parameter will be derived through an algorithm of combined data from Heatflux sensor and PPG signal. Diurnal patterns of core body temperature as well as the time of lowest daily temperature will be derived from this data.

Breathing rate and oxygen saturation

Breaths per minute count and oxygen saturation (%SpO₂) will also be derived from the Cardiowatch 287-2. Data will continuously be measured throughout the study period.

Objective sleep quality

Objective sleep quality will be monitored with the Withings Sleep Analyzer (Withings, Issy-les-Moulineaux, France) and an accelerometer (Corsano Cardiowatch 287-2 (Corsano Health, The Hague, the Netherlands), see text below). Prior to the study, the Withings Sleep Analyzer will be installed in the participants bed. A smart phone is required to set-up the device and the devices must be connected to a Wi-Fi to be able to send data to the cloud. After set-up no link to the smartphone is required. The device must be connected to power.

Objective physical activity

To monitor objective physical activity, Raw accelerometry will be derived from the Corsano Cardiowatch 287-2 (Corsano Health, The Hague, the Netherlands) on their right wrist during the entire study period. Raw data will be collected at 32Hz and will be derived from the wristband similar to the variable heart rate monitoring and HRV.

Food capturing

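### The hourly core temperature pattern, listed as a clock-function endpoint, includes the exercise hours, so morning and evening can differ without any clock shift

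*Combined protocol and SAP*

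**What the plan says.** The secondary objective (Section 2) includes "rhythmic parameters of biological clock function". Sections 8.1.2 and 10.2 both place core body temperature under the biological clock heading, with two sub-endpoints: the diurnal pattern and the time of lowest temperature.

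Section 8.3.3 describes the signal. "Participants will wear the wrist band 24 hours a day", and the temperature value is computed, not measured directly: "This parameter will be derived through an algorithm of combined data from Heatflux sensor and PPG signal". It continues: "Diurnal patterns of core body temperature as well as the time of lowest daily temperature will be derived from this data".

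Section 10.2 sets the analysis: "Diurnal patterns will be calculated through the hourly mean level of for example glucose and will be displayed for each condition". Active morning is compared with active evening, each is compared with the sedentary period as a sensitivity analysis, and, assuming normality, "a paired t-test will be used for all analyses". Section 10 adds line graphs to "visually inspect pattern differences between interventions", and a general rule: "Missing data will be interpolated/imputed with a standard algorithm".

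Section 5.1.1 puts the exercise hour at 10:00-11:00 or 19:30-20:30. Section 3 says that the calibration and measurement weeks differ only in the measurements, so exercise goes on while temperature is being recorded for analysis.

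No section excludes the exercise or recovery hours from the temperature pattern, adjusts for activity, or names the pattern parameter to be tested.

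**The concern.** Exercise raises body temperature directly, whatever the clock is doing. Here the exercise hour is the factor being compared, so the direct effect falls at different clock times in the two conditions. Hourly means that keep those hours carry it straight into the contrast. Randomised order, within-person comparison and a larger sample do not remove it.

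A pattern difference shown or tested under the clock-function heading could then be taken as evidence that exercise timing moved the clock, when it reflects only the hour in which the participant was exercising. The sensitivity comparisons with the sedentary period share the problem, because only one side of each contains an exercise hour.

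**Working it through.** **1. What can be reproduced.** The documents give no figure for core temperature. Their only size calculation is for the ISI (Section 4.4): 2.6 / 5.4 = 0.481. A two-sided paired t-test at 0.05 has power 0.790 at n = 35 and 0.802 at n = 36, so the stated 36 reproduces, and 40 × 0.9 = 36. I use it here only as the number of completers.

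**2. Assumptions (not in the documents).** No true clock shift; a rise of 0.2-0.5 °C in the derived temperature; no recovery tail unless stated; exercise on 5 of 7 measurement days (half of the eight club sessions, plus the Saturday home session; range 4-7).

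**3. Difference in the 10:00 hour.** Difference = rise × (days / 7) × shape. Shape is 1 if the full rise is immediate and 0.5 if it builds linearly over the hour.

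| Rise | Immediate | Linear |
|---|---|---|
| 0.2 °C | 0.2 × 5/7 = 0.14 °C | 0.07 °C |
| 0.5 °C | 0.5 × 5/7 = 0.36 °C | 0.18 °C |

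Morning is the warmer condition in that hour. With 4 to 7 days, the immediate case runs from 0.2 × 4/7 = 0.11 to 0.5 × 7/7 = 0.50 °C. The evening session straddles two hourly bins, so with an immediate rise the 19:00 and 20:00 hours each differ by half the 10:00 amount, 0.07-0.18 °C, with evening warmer. Against the sedentary period, active morning shows the same 10:00 difference.

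**4. What a paired t-test on that hour would do.** The plan does not specify this test; it is an illustration. The noncentrality is (difference / SD) × √36, with 35 degrees of freedom. The SD of the paired difference is assumed to be 0.2, 0.3 or 0.4 °C.

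| Rise, shape | SD 0.2 | SD 0.3 | SD 0.4 |
|---|---|---|---|
| 0.2 °C, linear | 0.55 | 0.28 | 0.18 |
| 0.2 °C, immediate | 0.99 | 0.79 | 0.55 |
| 0.5 °C, linear | 1.00 | 0.93 | 0.74 |
| 0.5 °C, immediate | 1.00 | 1.00 | 1.00 |

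Entries are the probability of p < 0.05 from exercise alone. A device response of only 0.1 °C, if immediate, gives the same figures as the first row (0.1 × 5/7 = 0.07 °C); smaller responses give less.

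**5. Time of lowest temperature.** With an assumed amplitude of 0.4 °C and peak at 17:00, the low point is near 05:00, far from both sessions. With an exponential recovery of time constant 1.5 h it moves by at most 0.03 h; with 3 h, by about 0.2 h.

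**6. What removing the hours achieves.** A 2 h buffer removes 10:00-13:00 and 19:30-22:30, which is 6 of 24 hours. With no tail, the false shift in a fitted peak is 0. With the 1.5 h tail and an immediate rise, a single cosine fitted to all hours shows a false shift of 0.48-1.16 h; after removal it is 0.11-0.27 h. A curve with 24-h and 12-h terms still leaves 0.26-0.67 h in the time of its peak.

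**7. DLMO as the alternative marker.** Section 8.3.4 has swabs on day 13 from 5 h before to 1 h after bedtime, in dim light. An assumed 22:00 bedtime gives 17:00-23:00, and 24:00 gives 19:00-01:00. Both contain the whole 19:30-20:30 session.

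**The case against.** The strongest reply is that the plan never says a temperature-pattern difference will be read as a phase shift. The link is a list heading; the endpoints are secondary and exploratory; Section 10 presents patterns descriptively; and a curve that includes the exercise hour is a fair description of each condition. Time of lowest temperature and DLMO are listed separately, and the sedentary comparison would help a reader see where a difference sits. That limits the weight of the point. It does not remove it: Section 10.2 makes the pattern an endpoint under clock function and applies the paired t-test to all analyses, and the sedentary comparison shows the exercise effect without adjusting for it.

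The quoted sentence names glucose, not temperature. Glucose is only an example, and Sections 8.3.3 and 10.2 both make core temperature a diurnal pattern.

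A reader might infer that exercise alone would almost certainly give a significant result. The documents do not support that. They give no temperature response, do not say how the heat-flux and PPG algorithm behaves during exercise, and specify no test on a single hour. For the same 0.2 °C rise, the probability is 18-55% or 55-99%, depending only on how fast the rise builds.

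A reader might also extend the point to heart rate. Section 10.2 classes heart rate as physiological, so its response to exercise belongs to that endpoint.

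**Conclusion.** The point holds for the core temperature diurnal pattern only. As written, the morning-evening contrast, and each active-sedentary contrast, mixes any clock effect with the direct effect of exercise, and nothing in the plan separates them. This rests on the design and on the absence of an exclusion rule, not on the simulated sizes.

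The size is unknown. Under the stated assumptions it is about 0.07-0.36 °C in the 10:00 hour, and less if the device responds weakly.

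It would be wrong to infer that the trial's main conclusion, or all of its clock measures, are compromised. The ISI does not use this signal, the time of lowest temperature hardly moves, and DLMO comes from saliva. DLMO has its own unresolved overlap with the evening session, so it cannot simply be taken as the clean substitute. Severity: minor to moderate.

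**What to change.** In Section 10.2, for core temperature only:

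1. State that the full 24-hour pattern is descriptive, includes direct exercise effects and is not read as a clock shift. Plot it with both exercise windows marked.
2. For any temperature-pattern comparison read as clock function, exclude the same clock times in all three conditions: both exercise windows plus a prespecified recovery buffer. Do this before hourly averaging, and state that the Section 10 imputation does not refill the gaps. Name one parameter for the paired t-test and vary the buffer as a sensitivity analysis. The type of fit and the buffer length are for the trial statistician to choose.
3. Make time of lowest temperature the main temperature-based clock measure. DLMO may stand beside it once the documents reconcile the day-13 dim-light swab window with the 19:30-20:30 session.

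No new data are needed. The cost is precision: with a 2 h buffer and independent residuals, the standard error of one participant's fitted peak rises by about 30% with a single cosine and 38-41% with two terms. Slow recovery can still leave a residual false shift (step 6 of the working), so the masked pattern should be supportive only. If the team wants no clock reading of the pattern at all, item 1 with item 3 is enough.
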